### Biospecimens

Collection of blood samples. When multiple groups are involved copy and paste the appropriate section below for example repeat section b when drawing blood from children and adults with cancer.

a. **From healthy, non-pregnant, adult subjects who weigh at least 110 pounds.** For a minimal risk application, the amount of blood drawn from these subjects may not exceed 550ml in an 8 week period and collection may not occur more frequently than 2 times per week.

Volume per blood draw: \_\_\_\_\_ ml

Frequency of blood draw (e.g. single draw, time(s) per week, per year, etc.) \_\_\_\_\_

b. **From other adults and children considering age, weight, and health of subject.** For a minimal risk application, the amount of blood drawn from these subjects may not exceed the lesser of 50 ml or 3 ml per kg in an 8 week period, and collection may not occur more frequently than 2 times per week.

Volume per blood draw: \_\_\_\_\_ ml

Frequency of blood draw (e.g. single draw, time(s) per week, per year, etc.) \_\_\_\_\_

Prospective collection of biological specimens other than blood: \_\_\_\_\_

### Review of medical records, images, specimens

Check all that apply (data includes medical records, images, specimens).

Only data that exists before the IRB submission date will be collected.

**Date Range for Specimens and/or Review of Medical Records:**

Examples: 01/01/1999 through 12/31/2015, or all records through mm/dd/yyyy.

Note: The Date Range must include the period for collection of baseline data, as well as follow-up data, if applicable.

The study involves data that exist at the time of IRB submission **and** data that will be generated after IRB submission. Include this activity in the Methods section.

Examples

- The study plans to conduct a retrospective chart review and ask subjects to complete a questionnaire.
- The study plans to include subjects previously diagnosed with a specific disease and add newly diagnosed subjects in the future.

The study will use data that have been collected under another IRB protocol. Include in the Methods section and enter the IRB number from which the research material will be obtained. *When appropriate, note when subjects have provided consent for future use of their data and/or specimens as described in this protocol.*

Enter one IRB number per line, add more lines as needed

Data    Specimens    Data & Specimens \_\_\_\_\_

Data    Specimens    Data & Specimens \_\_\_\_\_

Data    Specimens    Data & Specimens \_\_\_\_\_

### Data Analysis

*Power analyses may not be appropriate if this is a feasibility or pilot study, but end-point analysis plans are always appropriate even if only exploratory. Provide all information requested below, or provide justification if not including all of the information.*

#### Data Analysis Plan:

We hypothesize that efficacy of galvanic vestibular reduction to reduce motion sickness severity will depend on the timing of the administration, being more effective when administered prior to stimulus (symptom) onset. For specific aim 1 we will use repeated measures ANOVA to examine changes in symptom severity, test duration (terminated at moderate nausea), and recovery to baseline across three levels: prior to stimulus (symptom) onset, following symptom onset, and placebo control. For specific aim 2 we hypothesize that functional task performance will decline with increasing levels of galvanic vestibular reduction amplitude. We will use repeated measures ANOVA to examine changes in cognitive performance, dynamic posturography, and dual tracking performance across up to 5 levels of GVR amplitude. Sample size estimates are based on: (1) the expected variability ( $s^2$ ) in the response parameters, (2) the alpha ( $\alpha$ , type I) error level, or probability of incorrectly concluding there is an effect when responses are equivalent, (3) the magnitude of the effects to be detected between the means ( $\mu_1, \mu_2$ ), and (4) the certainty (statistical power,  $1 - \beta$ ) with which the effect is to be detected. Sample sizes can be calculated based on the expected standardized differences ( $\Delta$ ) between conditions (Fisher and Van Belle 1993).

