**Protocol:**

Participants will attend four sessions of the experiment on four separate days. The first/initial session will be required to establish galvanic vestibular sensitivity measures to customize the GVR level, and to characterize performance on a sensorimotor-cognitive test battery as a function of GVR stimulus level. In the next three sessions, we will test the efficacy of GVR to mitigate motion sickness by comparing conditions across three separate counterbalanced sessions: administration from the onset of testing, at a midpoint of testing, and placebo control. Each session will be conducted on four separate days at least two days apart so that there is no influence on each other. Using a repeated measures design, we will compare motion sickness symptom onset, severity and recovery during standardized motion sickness testing using a rotatory chair.

**Equipment:** The motion sickness experiments will be conducted using our GyroStim Multi-Axis Rotating Chair (used in the previous IRB approved project – IRB # 19-003257) located in Aerospace Medicine and Vestibular Research Lab at Mayo Clinic Arizona (Figure 1A). Subjects will be restrained in a chair but free to bend their head forward to elicit Coriolis cross-coupling stimuli. Subjects will be tested with their eyes closed. Galvanic

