vestibular reduction will be delivered using a proprietary system developed at the Mayo clinic laboratory. This utilizes a two-channel commercial galvanic stimulator (Good Vibrations Engineering Ltd, King City, ON; used in the previous IRB approved projects – IRB # 19-003257, 18-005564, 14-003906, 11-007718, 09-003815) with custom software. The GVR system consists of the four electrodes (two behind each ear). The stimulator can bidirectionally deliver the electrical stimulation and receive information about the amplitude delivered accounting for skin impedance. In addition to motion sickness reporting, we also propose to quantify the magnitude of the motion perception during the Coriolis cross-coupling protocol using a multidimensional joystick (Figure 1B, Logitech® FreedomTM 2.4; used in the previous IRB approved projects – IRB # 19-003257, 18-005564). Before the start of the experiment, participants will be trained to use joystick in cyclic sideways left/right, forward/backward and twist counterclockwise/ clockwise for the perceived roll, pitch and yaw motions respectively. The perceived motion inputs from the joystick will be recorded by the custom software program named AVATAR which will also display the animation of 3D graphical human figure based on joystick inputs (Figure 1C).

[figure not shown]

Figure 1: A. Aerostim Multi-Axis Rotating Chair, Ultrathera Technologies, B. 360° Wireless Joystick, Logitech® FreedomTM 2.4; C. AVATAR software that display the animation of 3D graphical human figure based on joystick inputs

**Motion sickness test paradigm:** At the beginning of each motion sickness session, the rotator will be accelerated (10 deg/sec/sec) to a constant velocity up to 120 deg/sec for up to 60 sec to allow the per-rotatory sensations to decay. The direction of rotation will be alternated each session and counterbalanced across subjects. Head

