movements will be cued every 10 sec, alternating between pitch forward (chin resting on chest) and pitch backward (head upright). This timing allows for subjects to use the joystick to record motion perception associated with each pitch forward and backward movement. There will be a short pause following each set of 9 forward/backward movements (3 min) to review symptoms with the subject, although motion sickness symptoms will be obtained throughout the test protocol using verbal reports. Subject will continue making head movements until the motion sickness endpoint (moderate nausea) or the maximum number of paired forward/backward head movements (90) has been reached.

**Galvanic Vestibular Reduction (GVR) application:** We will use a repeated measures design to compare motion sickness severity for each subject across the three treatment interventions: prior to stimulus onset, following symptom onset, and placebo control. For each session, the participant will be instrumented for GVR prior to rotation. The amplitude (up to 2.5 mA) will be customized based on individual sensitivity (see below). The order of the three sessions will be counter-balanced across subjects. For the “*prior to*” session, the GVR will be initiated just prior to the chair motion. For the “*midpoint*” session, the GVR will be initiated following 4 of 10 sets of movements or the onset of slight nausea, whichever occurs first. For the “*control*” session, the subject will be instrumented without turning on the GVR throughout the testing.

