**Motion sickness recordings:** Objective measures of sickness will be obtained using electrogastrography (EGG) methodology that we've employed successfully in previous motion sickness studies (Cevette et al. 2014a) (IRB # 18-005564, 14-003906). The EGG measurements will require seated baseline reading for approximately 20 mins prior to rotation. We propose up to three alternate methods for subjective reporting (to be finalized during pilot testing). First, an acute score will be derived using the Pensacola diagnostic criteria introduced by Graybiel et al. (1968). Using this scale, the subjective intensity of eight different modalities of symptoms and signs are reported on a “slight/moderate/severe” basis, and then numerically to arrive at a weighted “malaise index”. We will also obtain a subjective magnitude estimation score using a scale 0-20, with 20 indicating vomiting (Oman et al. 1986). And finally, participants will be asked to quantify motion sickness severity along multiple dimensions (e.g., gastrointestinal, central, and peripheral symptoms, Gianaros et al. 2001) using a multi-point scale for each.

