**Table II – Next three sessions (Prior, Mid-point, and Control Sessions)**

### Subject Information

*Target accrual is the proposed total number of subjects to be included in this study at Mayo Clinic. A “Subject” may include medical records, images, or specimens generated at Mayo Clinic and/or received from external sources.*

Target accrual: 40 participants

Subject population (children, adults, groups): Healthy adults with normal vestibular function

Inclusion Criteria: For our purposes, participants must be able to consent to participate themselves and be 21 to 55 years of age and must be able to attend in-person sessions at the Mayo Aerospace Medicine and Vestibular Research Laboratory in Scottsdale, AZ. No racial/ethnic groups will be excluded, although all participants must be fluent speakers of English.

Exclusion Criteria: History of vestibular disease, migraine, or significant balance disorder; traumatic brain injury, recent middle ear infection or recent motion sickness (within 72 hrs), history of severe motion sensitivity, women who are pregnant.

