#### Power Statement:

Standardized mean differences of 0.75 will be considered operationally relevant effect sizes for this comparison based our previous motion sickness mitigation protocols using the oculovestibular recoupling methodology

(Cevette et al. 2012). Based on the equation above, we will have 80% statistical power to detect standardized mean differences (two-sided tests) of 0.75 with an alpha error level of 0.05 with a sample of 16 subjects. A target of at least 30 subjects is requested to account for incomplete data sets.

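### Aim 1's repeated measures ANOVA has no term for session order or rotation direction and no rule for missed sessions; a mixed model on all sessions would be a cheap, optional improvement

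*Combined protocol and SAP*

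**What the plan says.** - **Model.** Data Analysis Plan: "For specific aim 1 we will use repeated measures ANOVA to examine changes in symptom severity", along with test duration and recovery. The one factor is condition, at three levels (prior, midpoint, control).
- **Session order.** Galvanic Vestibular Reduction (GVR) application: "The order of the three sessions will be counter-balanced across subjects". The number of orders is not given.
- **Rotation direction.** Motion sickness test paradigm: "The direction of rotation will be alternated each session and counterbalanced across subjects".
- **Spacing.** The Protocol paragraph puts sessions "at least two days apart so that there is no influence on each other". No check of that assumption is named.
- **Incomplete data.** The Power Statement derives 16 participants for 80% power at a standardized difference of 0.75 (two-sided, alpha 0.05), then says: "A target of at least 30 subjects is requested to account for incomplete data sets". Subject Information gives "Target accrual: 40 participants".

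The documents do not say how a participant with only one or two of the three sessions is analysed.

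**The concern.** The design balances two nuisance factors, but the analysis uses neither. If severity drifts over sessions, for example through habituation, an ANOVA on condition alone leaves that drift in its error term.

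The plan answers expected incompleteness by enrolling more people, not with an analysis rule. A repeated measures ANOVA in its usual form needs all three scores, so someone who came for one or two provocative sessions would contribute nothing. What is at stake is mainly efficiency: data already collected, at some discomfort to participants, would go unused.

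**Working it through.** **1. The plan's own figure.** Read 0.75 as the mean difference divided by the SD of the paired difference.

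- Normal approximation: ((1.960 + 0.842)/0.75)² = 13.95.
- With the small-sample term 1.960²/2 = 1.92: 15.87, so 16.
- Exact noncentral t power at n = 16: 80.06%. With all participants complete it is 97.8% at 30 and 99.6% at 40.

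The 16 and the 80% are confirmed. Going from 30 to 16 leaves room for 14/30 = 47% incomplete. That is the whole margin, not a documented dropout rate.

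**2. Effect of leaving out a session trend.** Take six balanced orders and a drift of s per session, in SDs of the paired difference. Two conditions are one session apart in four orders and two apart in two, so the mean squared gap is (4×1 + 2×4)/6 = 2. The error variance used for a paired contrast is therefore multiplied by 1 + 2s².

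- s = 0.1, 0.3, 0.5 gives 1.02, 1.18, 1.50.
- Paired-t power: 79%, 73%, 63% with 16 complete; 98%, 96%, 90% with 30 complete.

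The estimate stays unbiased and the test becomes conservative.

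**3. Sessions discarded by complete-case analysis.** Assume half of the incomplete participants miss session 3 and half miss sessions 2 and 3.

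- 30 enrolled, 14 incomplete: observed 16×3 + 7×2 + 7×1 = 69; discarded 14 + 7 = 21.
- 40 enrolled, 19 incomplete (about the same share): 28 of 91 or 29 of 92, depending on how the odd participant falls.

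**4. Power for prior versus control, by simulation.** All settings are assumptions: Gaussian score with no ceiling, true effect −0.75, within- and between-participant variance 0.5 each (so paired-difference SD = 1), midpoint effect half of prior, equal correlations, loss at random. The mixed model here has a random participant intercept plus condition, session number and direction. Habituation is per session, in within-participant SDs; 0.5 of these is 0.5×√0.5 = 0.354 in the units of step 2. Ranges are the spread over separate runs.

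| Enrolled | Incomplete | Habituation | Complete-case ANOVA | Mixed model |
|---|---|---|---|---|
| 30 | 5 | none | 96% | 96–97% |
| 30 | 10 | none | 90% | 94% |
| 30 | 14 | none | 81–83% | 91% |
| 30 | 14 | 0.5 SD | 75–77% | 91–92% |
| 40 | 10 | none | 98% | 99% |
| 40 | 19 | none | 92% | 97% |
| 40 | 19 | 0.5 SD | about 86% | 96–97% |

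Most of the gain comes from using all sessions. With 30 enrolled and 14 incomplete, a mixed model on condition alone gives 92% without habituation and 88% with 0.5 SD. The session and direction terms then cost about 1 point or add about 3 to 4.

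**5. The equal-correlation assumption.** The midpoint session starts without GVR, as control does (Table II), so midpoint and control scores may correlate more strongly than the other pairs. With unit variances, a paired difference has variance 2(1 − ρ), and a pooled error averages the three pairs.

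- ρ = 0.7 for midpoint–control, 0.5 otherwise: pooled (0.6 + 1.0 + 1.0)/3 = 0.867 against a true 1.0 for prior–control. The cut-off 1.96×√0.867 = 1.82 gives about 6.8% false positives.
- ρ = 0.8 and 0.4: pooled (0.4 + 1.2 + 1.2)/3 = 0.933 against 1.2. The cut-off 1.96×√0.778 = 1.73 gives about 8.4%.

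Simulation under such assumed correlations gives about 7–9% for both the pooled-error ANOVA and the random-intercept model, and about 5% for a paired t test.

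**6. Ceiling.** Stopping at moderate nausea may cap severity. With 30 enrolled, 14 incomplete, no session effect and a cap at the control mean +1, +0.5 or 0 SD, both estimates shrink to −0.69, −0.60 and −0.48. Power is 81% versus 90%, 78% versus 88%, and 71% versus 82%.

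**The case against.** The strongest reply is that nothing is broken. Order and direction are handled by design, sessions are spaced, and enrolment is raised from 16 to at least 30, with accrual of 40, precisely for incomplete data. Complete-case deletion is an inference. Incomplete data could also mean lost recordings or unfinished Aim 2 batteries, in which case fewer sessions are missing. The visible gains need nearly half of the participants to be incomplete. All of this stands, and it is why the change is optional.

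Four stronger readings are tempting but unsupported:

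- **The trial is underpowered, or 16 is wrong.** The figure reproduces, and enrolment covers heavy loss.
- **Omitting order and direction biases the result or inflates false positives.** With balanced orders the contrast is unbiased. With equal correlations the ANOVA rejected 1.4% to 5.1% under no effect. The inflation in step 5 comes from unequal correlation, not from the omitted terms.
- **The mixed model removes dropout bias.** When non-return depends on the last observed score, it does better (−0.75 against −0.72, or −0.69 with habituation). When it depends on the unseen next score, it does slightly worse (−0.71 against −0.72 to −0.75). The documents do not say which applies.
- **Sessions influence each other.** Nothing shows this. Were carryover unequal (0.5 SD after control), both methods would give −0.87 instead of −0.75.

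It would equally be wrong to infer that the ANOVA keeps 80% in all but extreme cases: step 6 gives 78% and 71% with no session effect.

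**Conclusion.** The point holds as a low-cost improvement, not as an error. The plan names no order or direction term and no missing-session rule. Using all sessions gains at most about 1 point of power with light loss, roughly 8 to 10 points with 14 of 30 incomplete, and about 14 to 17 points if habituation of 0.5 SD is added. At 40 enrolled with 19 incomplete the gain is about 5 points, or 10 to 11 with that habituation.

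These sizes rest on assumed loss rates, random loss, equal correlations and an uncapped Gaussian score; none is documented. They were obtained with a random-intercept model, so they are indicative for the more flexible covariance recommended below. Neither method is assured of 80% if stopping caps severity.

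**What to change.** For Aim 1 symptom severity, amend the Data Analysis Plan as follows:

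- Name one severity scale and one per-session summary. Motion sickness recordings leaves up to three scales open, and Table II scores every set.
- Make the main analysis a linear mixed model on all available sessions, with fixed effects for condition, session number and rotation direction, fitted by REML with Kenward-Roger degrees of freedom.
- Use an unstructured within-participant covariance by condition, or an error specific to each pair of conditions, in place of a random intercept alone.
- Report the session effect with its 95% CI.
- Keep the complete-case repeated measures ANOVA as a sensitivity analysis.
- State the limits: the model assumes missing at random and corrects neither unequal carryover nor a ceiling. It is not proposed for test duration, which is capped.

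The cost is wording and a little analysis work, with no extra participants or data. Session number and direction use three degrees of freedom. With 16 complete participants and no session effect, the random-intercept model gave about 82% against 82.5–84% for the ANOVA, so about 1 to 2 points; with a ceiling at the control mean it was 69.7% against 71.2%. A pair-specific error has its own price when correlations are in fact equal: at n = 16 the paired t test has 80.1% against 82.7% with pooled error, or 2.6 points. A sponsor who prefers the ANOVA should at least state how participants with missing sessions are handled.

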### Research Question and Aims

Hypothesis:

1. The efficacy of galvanic vestibular reduction to reduce motion sickness severity will depend on the timing and magnitude of the administration.
2. The functional task performance will decline with increasing levels of galvanic vestibular reduction.

Aims, purpose, or objectives:

Alterations in vestibular sensory processing following G-transitions lead to perceptual and motion sickness upon return to Earth's gravity. The use of a non-pharmaceutical mitigation for motion sickness will have several potential advantages over drug treatment options. First, the treatment would be effective immediately and for as long as needed without having to maintain therapeutic levels in the blood-stream. Second, the treatment level could be customized and continuously titrated during re-adaptation to minimize side effects while enhancing performance. Our project will validate a non-pharmaceutical tool using galvanic vestibular reduction (GVR) to better mitigate G-transitional induced motion sickness following symptom onset while customizing the treatment level to maximize crew performance.

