effects that impact functional ability. In order to leverage our non-pharmaceutical technique that allows continuous adjustments in “dosage” level throughout recovery, we must map changes in GVR level with functional performance. Our second hypothesis is that functional task performance will decline with increasing levels of galvanic vestibular reduction. We will test this hypothesis by measuring performance on a sensorimotor and cognitive test battery in steps ranging from 0mA (control) to the level of GVR thought to provide maximal motion sickness protection. The test battery, conducted on the same subjects as specific aim 1, will include dynamic posturography as well as other cognitive and flight simulator tasks. Sensitivity to galvanic stimulation will also be obtained for each subject and used to customize the GVR amplitude for the motion sickness testing in specific aim 1. The combined deliverable from both specific aims will be to validate the efficacy of GVR when customizing the stimulus level and introducing it following symptom onset, and to understand the effects of this non-pharmaceutical approach on crew performance on functional task performance.

**Background** (*Include relevant experience, gaps in current knowledge, preliminary data, etc.):*

The rationale of our approach rests on several key principles. First, the incidence and severity of motion sickness following G-transitions poses substantial risk to the deconditioned crew during landing and subsequent recovery operations. Second, there is a well-known relationship between bilateral vestibular loss and insusceptibility to motion sickness. Third, non-pharmaceutical approaches to motion sickness mitigation typically involve vestibular habituation or desensitization training with limited retention. Fourth, galvanic vestibular reduction provides a means to mitigate motion sickness following long-duration spaceflight without dependency on retention of preflight desensitization training.

Space motion sickness represents one of the greatest clinical challenges impacting crew activities during the first few days on orbit. While the inflight incidence has varied with different spacecraft, approximately 70% experience symptoms (Lackner and Dizio 2006) and one-third experience moderate to severe symptoms (Reschke et al. 2016). Symptoms generally last 2-3 days inflight, although symptoms may persist in a small number of people (Baker et al. 2008).

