function during flight. The primary task during the flight simulation will be to fly through the “ring target”. The cognitive test will include Mayo’s proprietary Ocular Cognitive Addition Test (OCAT, Pradhan et al. 2019) which requires subjects to look for numbers on a screen and add these numbers together. The OCAT test includes eye-tracking to measure cognitive and oculomotor performance measures (used in previous IRB approved projects – IRB # 18-005564, 18-004184, 19-004883, 16-007938). Each test will be repeated for up to GVR amplitudes (including 0mA control) presented in random order. OCAT will be conducted on a 14-inch tablet with an integrated eye-tracking sensor (EyeOn – EyeTech Digital Systems). We expect performance to decline with increasing GVR amplitude.

**Galvanic vestibular sensitivity:** We will compare motion perception at different GVR amplitudes using a similar rotator protocol as described above for the motion sickness testing. Motion perception will be quantified using the joystick. The GVR amplitudes (same range as above) will be presented in random order. Assuming a saturation effect, we will select the lowest GVR level that reduces motion perception as the amplitude for the motion sickness testing above.

A complete experimental methodology to be conducted in this protocol is shown the tables below:

Visit 1	Duration (mins)
Consent form	
Balance Performance (Dynamic Posturography): Device: Bertec Portable Essential's dual-balance plate balance system ( https://www.bertec.com/bertec-balance-advantage-systems )  Quantify dose-response for the following GVR amplitudes: Standing Eyes Open – 0mA (baseline), 1.25mA, 1.5mA, 1.75mA, and 2mA Standing Eyes Closed - 0mA (baseline), 1.25mA, 1.5mA, 1.75mA, and 2mA	10
Timed up and go (TUG):  The test will be performed for each GVR amplitudes: 0mA (baseline), 1.25mA, 1.5mA, 1.75mA and 2mA  Method: 

• The patient starts in a seated position

• The patient stands up upon on command: walks 4 meters, turns around, walks back to the chair and sits down.

	10

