
 
• An obstacle (foam block 30 cm height) will be positioned between the chair and the 4m turning point, and the patient will be required to step over this obstacle twice, once on the way toward the turning point and again on the return back.
 
• The time stops when the patient is seated.
 
	

Cognitive Performance  Device: Oculo-Cognitive Addition Test (OCAT):  0mA (baseline), 1.75mA (GVR)
	5

Galvanic Vestibular Sensitivity:  Device: Gyrostim Rotating Chair and Joystick  The chair will be rotated for up to 60 seconds with an acceleration of 10 deg/s/s to a constant velocity up to 120 deg/sec and deceleration of 10 deg/s/s to a complete stop.  5 trials of rotations will be tested for each GVR amplitudes:  0mA (baseline), 1.25mA, 1.5mA, 1.75mA and 2mA  The GVR will be turned on before each corresponding rotation.  1 minute washout period after each rotation.  Motion perception (i.e., yaw) will be measured using the joystick for each rotation.  Decide the lowest GVR amplitude that reduced motion perception, say R mA.
	20

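### The planned Aim 2 ANOVA ignores dose order and direction, so a significant result could be read as graded decline when performance differs only between 0 mA and active stimulation

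*Combined protocol and SAP*

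**What the plan says.** Under Research Question and Aims, Hypothesis 2 reads: "The functional task performance will decline with increasing levels of galvanic vestibular reduction". The second specific aim gives the reason: because GVR can be adjusted continuously during recovery, "we must map changes in GVR level with functional performance". The test battery section adds that the aim is to learn how crew could titrate amplitude.

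The Data Analysis Plan repeats the ordered hypothesis ("functional task performance will decline with increasing levels of galvanic vestibular reduction amplitude") and then names one method: "repeated measures ANOVA to examine changes in cognitive performance, dynamic posturography, and dual tracking performance across up to 5 levels of GVR amplitude". It gives no trend contrast, no model with amplitude as a quantity, no comparison among active levels, no direction, and no rule for declaring the hypothesis supported.

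The levels are in Table I (first visit):
- Posturography: "Quantify dose-response for the following GVR amplitudes", with, for example, "Standing Eyes Closed - 0mA (baseline), 1.25mA, 1.5mA, 1.75mA, and 2mA".
- Timed up and go (TUG): "The test will be performed for each GVR amplitudes: 0mA (baseline), 1.25mA, 1.5mA, 1.75mA and 2mA". TUG is not among the outcomes in the Data Analysis Plan.
- Oculo-cognitive addition test (OCAT): two levels only, 0 and 1.75 mA.
- Dual tracking, which the Data Analysis Plan lists, has no row in the table.

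The Power Statement covers a difference between two conditions: 0.75 standardized, two-sided alpha 0.05, 80% power, 16 subjects, with at least 30 requested. Subject Information gives a target accrual of 40.

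**The concern.** The hypothesis is about an ordered decline, whereas the test asks only whether any level differs from any other. Two patterns with different meanings for titration can both give a significant result. If performance falls with each increase in amplitude, a lower active level costs less function. If performance drops once when the current is switched on and then stays flat, the choice of level within the active range makes no difference to function. The planned F test cannot separate the two, nor a decline from an improvement.

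The spacing of the levels adds to the difficulty. Nothing is tested between 0 and 1.25 mA, and the active levels then rise in steps of 0.25 mA. The natural repair, a linear trend over all five levels, therefore leans mostly on the 0 mA point.

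**Working it through.** **The plan's own figure.** For a paired comparison with standardized difference 0.75 and n=16, the noncentrality is 0.75 × √16 = 3.0 on 15 df. Two-sided power at 0.05 is 0.80 (0.77 at n=15). The stated 16 is reproduced, but for two conditions, not for a dose trend.

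**Assumptions, not in the documents.** Normal, independent trial errors with equal variance σ²; paired differences with SD 1, so 2σ² = 1 and σ² = 0.5. The 0.75 is carried over from motion sickness work because the plan gives no size for functional performance.

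**Overall F, pure on/off effect.** The level means are 0, −0.75, −0.75, −0.75, −0.75, with grand mean −0.60.
- Sum of squares: 0.60² + 4 × 0.15² = 0.36 + 0.09 = 0.45.
- λ = n × 0.45 / 0.5 = 0.9n, on 4 and 4(n−1) df.
- Probability of p<0.05: 0.85 at n=16 (λ=14.4) and 0.99 at n=30 (λ=27).

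**Overall F, decline linear in mA reaching −0.75 at 2 mA.** The slope is −0.375 per mA.
- Sum of squares: 0.375² × 2.425 = 0.341, so λ = 0.682n.
- Probability of p<0.05: 0.72 at n=16 and 0.96 at n=30.

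Both patterns are usually significant. In simulation at n=16 (20,000 replicates), the F test is also significant in 85% of trials for an on/off improvement of the same size. It is significant in 82% when performance is worst at 1.25 mA and back to baseline at 2 mA (0, −0.75, −0.5, −0.25, 0).

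**Linear trend over all five levels.** The mean of 0, 1.25, 1.5, 1.75 and 2 is 1.3. The squared deviations are 1.69, 0.0025, 0.04, 0.2025 and 0.49, which sum to 2.425. The 0 mA share is 1.69 / 2.425 = 70%. This trend correlates 0.93 with the contrast of 0 mA against the active mean. Under a pure on/off effect it signals decline in 91% of trials at n=16 and more than 99% at n=30.

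**Slope within the active levels.** The mean is 1.625 and the deviations are ±0.375 and ±0.125, so the sum of squares is 2 × (0.140625 + 0.015625) = 0.3125. The squared noncentrality is n × slope² × 0.3125 / 0.5. Under a pure on/off effect it is zero, and the test rejects at its nominal 5% (2.5% in the declining direction).

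| True pattern | Squared noncentrality | Power n=16 | n=30 | n=40 |
|---|---|---|---|---|
| Linear in mA (slope −0.375 per mA) | 0.088n | 0.20 | 0.35 | 0.45 |
| Equal steps 0, −0.1875, −0.375, −0.5625, −0.75 (slope −0.75 per mA among active levels) | 0.352n | 0.60 | 0.88 | 0.95 |

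**0 mA against the active mean.** The variance is 0.5 × (1 + 1/4) = 0.625.
- Linear decline: d = 0.375 × 1.625 / √0.625 = 0.77; power at n=16 is 0.82, against 0.72 for the overall F.
- Equal steps: d = 0.46875 / √0.625 = 0.59; power is 0.60, against 0.74 for the overall F.

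Which test is stronger depends on the shape.

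**Risk of the opposite error.** Suppose an on/off effect were concluded whenever the 0-versus-active contrast was significant and the slope was not. Under the linear decline above, which is truly graded, that conclusion would be drawn wrongly in about 66%, 64% and 55% of trials at n=16, 30 and 40.

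**The case against.** A fair defence is that the plan says only that ANOVA will be used to examine changes. No rule makes a significant F a confirmation of Hypothesis 2. Table I promises to quantify dose-response for posturography, so level means will presumably be reported and would show direction and any plateau. The tested range starts at 0 mA, so a fall from 0 to active levels is part of the hypothesis, and a plateau would not contradict it.

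Much of this stands. A reader might infer that the plan will declare graded decline from the F test, or that its Aim 2 conclusion will be wrong. The documents do not support that; the most they support is that a significant F could be read so. A reader might also infer that all Aim 2 outcomes have five levels. Of the three outcomes in the Data Analysis Plan, only posturography is scheduled that way; OCAT is listed as "0mA (baseline), 1.75mA (GVR"). The size 0.75 comes from motion sickness mitigation, and n=16 is the minimum, below the targets of at least 30 and 40.

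The defence does not supply a pre-specified quantity that addresses order or direction. Looking at means after a significant F is not a planned test of gradation, and titration within the active range needs one.

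**Conclusion.** The concern holds in limited form. The planned Aim 2 test is valid for any difference among levels, but it does not address the ordered, directional question that Hypothesis 2 and the titration purpose pose. The percentages rest on independent, equal-variance errors, a borrowed effect size and assumed dose shapes. That the test ignores order and direction rests on none of these.

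Two further readings should be resisted. First, a non-significant slope within 1.25 to 2 mA would not establish an on/off effect, given its low power if decline is linear in mA. Secondly, the contrasts are not a general gain in power: the advantage over the overall F belongs to the 0-versus-active contrast and reverses under equal steps. The argument is that each contrast answers a stated question. For OCAT, two amplitudes allow only an on-versus-off comparison, and no choice of analysis changes that.

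**What to change.** In the Data Analysis Plan, for outcomes measured at five amplitudes (posturography, and TUG if it is added to the analysis list), pre-specify two orthogonal contrasts, computed per participant and tested with a one-sample t test:

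- (a) 0 mA against the mean of the four active levels: coefficients −1, ¼, ¼, ¼, ¼.
- (b) the linear slope across 1.25, 1.5, 1.75 and 2 mA, using the actual mA values: coefficients 0, −0.375, −0.125, 0.125, 0.375, divided by 0.3125.

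Report both with 95% confidence intervals alongside the level means, and state the reading rules in advance:

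- Claim decline with increasing amplitude within the active range only if (b) shows it in the declining direction.
- If only (a) is significant, and in the direction of worse performance, conclude that performance is worse on active GVR than at 0 mA and that gradation within 1.25 to 2 mA is unresolved. Let the interval for (b) show how much gradation is excluded. Do not conclude an on/off effect from a non-significant slope.
- For OCAT, limit the conclusion to 1.75 mA against 0 mA.
- Draw no conclusion about the untested amplitudes between 0 and 1.25 mA.

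The cost is wording only, with no added visits, measurements or participants. The downside is a possibly less favourable claim: with the slope power shown above, a true graded decline may go undemonstrated, and the report would have to say so.
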